4.6 TREATMENT, PATIENT, STUDY, AND SITE DISCONTINUATION

4.6.1 Study Treatment Discontinuation

Please see the main study protocol for Study BN42082 for any study treatment discontinuation.

4.6.2 Substudy Discontinuation

Patients may discontinue from the substudy at any time, without affecting their participation in the main studies BN42082. Withdrawal from the substudy does not constitute withdrawal from the main studies.

Patients who discontinue treatment but are still being monitored in the main studies may still participate in the substudy for substudy assessments, even in the absence of treatment, or if taking alternate treatment(s).

If the patient wishes to withdrawal from the substudy and from the main study, please see the main study protocol for Study BN42082 for study treatment discontinuation.

In addition, the Sponsor maintains the right to terminate this substudy at any time. Reasons for terminating the study may include, but are not limited to, the following:

- The incidence or severity of adverse events in this or other studies indicates a potential health hazard to patients
- Patient enrollment is unsatisfactory

The Sponsor will notify the investigator if the Sponsor decides to discontinue the substudy.

4.6.3 Substudy Site Closure

The Sponsor has the right to close a site at any time. Reasons for closing a site may include, but are not limited to, the following:

- Excessively slow recruitment
- Poor protocol adherence
- Inaccurate or incomplete data recording
- Non-compliance with the ICH guideline for Good Clinical Practice
- No study activity (i.e., all patients have completed the study and all obligations have been fulfilled)

5. ASSESSMENT OF SAFETY

5.1 SAFETY PLAN

Please see the main study protocol for Study BN42082 for the details on the safety plan.

5.2 SUBSTUDY SAFETY PARAMETERS AND DEFINITIONS

Safety assessments for the substudy will consist of monitoring and recording AEs associated with any substudy procedure. All other assessments of safety should be monitored and recorded as part of the main study protocol for Study BN42082.

5.2.1 Adverse Events

According to the ICH guideline for Good Clinical Practice, an adverse event is any untoward medical occurrence in a clinical investigation subject administered a pharmaceutical product, regardless of causal attribution. An adverse event can therefore be any of the following:

- Any unfavorable and unintended sign (including an abnormal laboratory finding), symptom, or disease temporally associated with the use of a medicinal product, whether or not considered related to the medicinal product
- Any new disease or exacerbation of an existing disease (a worsening in the character, frequency, or severity of a known condition) (see Section 5.3.5.9 and 5.3.5.10 for more information)

- Recurrence of an intermittent medical condition (e.g., headache) not present at baseline
- Any deterioration in a laboratory value or other clinical test (e.g., ECG, X-ray) that is associated with symptoms or leads to a change in study treatment or concomitant treatment or discontinuation from study drug
- Adverse events that are related to a protocol-mandated intervention, including those that occur prior to assignment of study treatment (e.g., screening invasive procedures such as biopsies). Any adverse event related to a substudy procedure (LP, blood draw) should be reported as part of the BN42082 eCRF

Adverse events should be collected at any visit, including substudy visits.

5.2.2 Serious Adverse Events (Immediately Reportable to the Sponsor)

Please refer to the main study protocol for Study BN42082 for serious adverse event reporting.

5.2.3 Eliciting Adverse Event Information

A consistent methodology of non-directive questioning should be adopted for eliciting adverse event information at all patient evaluation timepoints. Examples of non-directive questions include the following:

"How have you felt since your last clinic visit?"

"Have you had any problems or issues with your lumbar puncture?"

5.2.4 Medical Monitors and Emergency Medical Contacts

Investigators will be provided with contact information for the Medical Monitor. To ensure the safety of study patients, an Emergency Medical Call Center will be available 24 hours per day, 7 days per week, in case the above-listed contacts cannot be reached. The Emergency Medical Call Center will connect the investigator with an Emergency Medical Contact, provide medical translation service if necessary, and track all calls. Contact information, including toll-free numbers for the Emergency Medical Call Center, will be distributed to investigators.

5.3 FOLLOW-UP OF PATIENTS AFTER ADVERSE EVENTS

Refer to the main study protocol for Study BN42082 for the details on the adverse event follow-up. All adverse events, including those specific to substudy procedures, will be followed up in the main studies.

6. STATISTICAL CONSIDERATIONS AND ANALYSIS PLAN

The objectives of this substudy are as follows:

- To compare the changes from baseline in levels of NfL and B-cells between the treatment arms
- To assess the relationship between biomarkers in CSF and blood and their correlation with efficacy outcomes
- To generate the hypotheses about biomarkers of ocrelizumab treatment in patients with RMS

Unless otherwise specified, statistical tests will be two-sided and the statistical significance level will be 5%. Corresponding 95% confidence intervals will be presented as appropriate. No corrections for multiple testing will be applied to the primary, secondary, exploratory endpoint analyses, or interim analysis.

The statistical summaries will be descriptive if not otherwise specified. For continuous variables, the mean, median, standard deviation, 25th and 75th percentiles, minimum and maximum will be calculated. For categorical variables, number and percentage in each category will be displayed.

When establishing statistical significance, parametric and non-parametric methods will be applied as appropriate. Primary endpoints will be analysed using Mixed Model Repeated Measures. Some variables may be appropriately transformed before performing statistical analysis. The Spearman's rank correlation coefficient will be used to evaluate the relationship among the levels of biomarkers and between levels of biomarkers and clinical parameters.

The analysis population will consist of all randomized patients with at least one substudy assessment.

Any additional analyses and full details of all statistical issues and planned statistical analyses will be specified in a separate Statistical Analysis Plan, which will be finalized prior to the database lock and unblinding.

6.1 DETERMINATION OF SAMPLE SIZE

The sample size calculations are based on NfL levels observed in the OBOE study (ML29966) at Week 52 ([Bar-Or et al. 2019](#)). Since NfL data are skewed, they will be log-transformed for the purposes of statistical analysis. Assuming a 1.5-fold reduction in NfL levels (pg/mL) between higher dose and approved dose groups, a common SD to be 0.32 (log10 scale), 80% power and 5% alpha, dropout rate of 20% by Week 48, the sample size required for the study is up to 144 RMS patients.

In case less than 144 patients will consent to participate in this substudy or a higher dropout rate is observed, the sample size required to observe a larger than 1.5-fold reduction in NfL levels is: 90 subjects – 2-fold reduction, 27 subjects – 2.5-fold reduction, 15 subjects – 4-fold reduction.

Based on the sample size requirements for changes in NfL levels, effect sizes for changes in number of B-cells which can be detected with 80% power were determined.

With the sample size of 144, 20% dropout at Week 48, and assuming a SD of 0.76 (log₁₀ scale) at Week 24 and 0.97 (log₁₀ scale) at Week 48, it would be possible to detect at least a 2.7- and 3.5-fold reduction in the levels of B-cells (cells/ μ L) at Week 24 and at Week 48, respectively.

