4.2 METHOD OF TREATMENT ASSIGNMENT AND BLINDING

4.2.1 Treatment Assignment

This is a randomized, double-blind study. After initial written informed consent has been obtained, all screening and baseline procedures and assessments have been completed, and eligibility has been established for a patient, the patient will be assigned an identification number and treatment assignment by an interactive voice or web-based response system (IxRS).

Patients will be randomly assigned to one of two treatment arms: higher dose or approved dose of ocrelizumab. Randomization will occur in a 2:1 ratio (higher dose to approved dose, respectively) through use of a permuted-block randomization method to ensure a balanced assignment to each treatment arm. Randomization will be stratified according to the following criteria:

- Weight at baseline (<75 kg vs. ≥75 kg)
- Region (United States vs. ROW)
- EDSS (<4 vs. ≥4)
- Age at screening (≤45 years vs. >45 years)

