4.2 METHOD OF TREATMENT ASSIGNMENT AND BLINDING

Refer to the main study protocol for Study BN42082.

4.3 STUDY TREATMENT AND OTHER TREATMENTS RELEVANT TO THE STUDY DESIGN.

Refer to the main study protocol for Study BN42082 for all information relating to formulation, packaging, dosage, administration, treatment discontinuation, compliance, handling, accountability and/or continued access to drug.

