## 2.2 SAMPLE SIZE DETERMINATION

The sample size was determined based on data from Studies WA21092 and WA21093 (Opera I and Opera II, respectively) and Kappos et al. (2018). A two-group test of equal exponential survival curves was used to determine the sample size for the time to onset of cCDP12. With a 2:1 randomization ratio between the higher and approved dose treatment arm and assuming recruitment of 390 patients per year, 5% annual dropout rate, a control group progression rate of 21.5% and 5% two-sided Type I error, it is predicted that a sample size of approximately 786 (524:262) patients will be required to achieve 80% power to detect a HR of 0.66 based on 205 cCDP12 events. Therefore, the DBT phase will run until at least 205 cCDP12 events are observed.

Between November 2020 and December 2021, a much faster recruitment rate was observed than anticipated and 798 patients were randomized. Of the 798 randomized patients, 116 and 135 patients were participating at sites in Ukraine and Russia, respectively. To mitigate a potential withdrawal of patients or loss of data from Ukraine and Russia, due to the current conflict in the Ukraine, starting in February 2022, 67 additional patients were randomized from April 2022 to August 2022 resulting in a total sample size of 865 patients (10% more than the planned sample size in the absence of the war) for this study.

Supplementary analyses have been proposed in Section 4.2.4 to investigate the impact of the Russia-Ukraine war on the primary analysis. Furthermore, analyses to assess the impact of the war on study conduct have been proposed in Section 4.6.3.

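### CSF substudy sample size: 90 subjects does not correspond to a 2-fold NfL reduction on the stated inputs; 2-fold needs about 42 evaluable patients, and 90 matches about 1.6-fold

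*Protocol*

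**What the plan says.** Protocol Appendix 18, Section 6.1, sizes the CSF substudy on NfL at up to 144 patients for a 1.5-fold difference between arms, with these inputs: "a common SD to be 0.32 (log10 scale), 80% power and 5% alpha, dropout rate of 20% by Week 48". For the case of fewer consenting patients or higher dropout, it then lists what smaller substudies could detect: "90 subjects – 2-fold reduction", followed by "27 subjects – 2.5-fold reduction, 15 subjects – 4-fold reduction". No other SD, power or alpha is given for this list.

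The remaining inputs are elsewhere:

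- Appendix 18, Section 6: "Unless otherwise specified, statistical tests will be two-sided and the statistical significance level will be 5"%.
- Appendix 18, Section 4.2, on treatment assignment: "Refer to the main study protocol for Study BN42082".
- Main protocol, Section 4.2.1: "Randomization will occur in a 2:1 ratio (higher dose to approved dose, respectively").
- Appendix 18, Section 6, on the planned analysis: "Primary endpoints will be analysed using Mixed Model Repeated Measures".

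**The concern.** The list looks uneven before any formal calculation. For a fixed SD, the required size varies roughly as one over the squared log10 difference. Going from 2-fold to 2.5-fold raises that difference from 0.301 to 0.398, so the size should fall by about 43% (1 − (0.301/0.398)² ≈ 0.43). The printed sizes fall from 90 to 27, which is 70%.

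CSF NfL at Week 48 is a primary endpoint of the substudy, and these sizes are the protocol's only statement of what a smaller substudy could show. As printed, a reader would conclude that 42 to 89 evaluable patients could not support a 2-fold comparison, when on the protocol's own inputs they could.

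**Working it through.** **Inputs.** SD = 0.32 (log10), power 80% and alpha 5% from Appendix 18, Section 6.1. Two-sided testing from Appendix 18, Section 6. Allocation 2:1 from main protocol Section 4.2.1, through Appendix 18, Section 4.2. The difference to detect is log10(fold).

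**Method.** Two-sample t-test using the noncentral t distribution, with noncentrality log10(fold) / (0.32 × √(1/n₁ + 1/n₂)). Arms are whole patients in an exact 2:1 split, and the size is the smallest total with power of at least 80%.

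| Fold reduction | log10 | Evaluable (2:1) | Power | Next smaller 2:1 total | Protocol prints |
|---|---|---|---|---|---|
| 1.5 | 0.176 | 80+40 = 120 | 80.5% | 117: 79.5% | 144 (= 120 × 1.2) |
| 1.6 | 0.204 | 60+30 = 90 | 80.6% | 87: 79.2% | not listed |
| 2 | 0.301 | 28+14 = **42** | 80.1% | 39: 76.9% | **90** |
| 2.5 | 0.398 | 18+9 = 27 | 83.3% | 24: 78.4% | 27 |
| 4 | 0.602 | 10+5 = 15 | 88.7% | 12: 79.0% | 15 |

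The calculation reproduces 144, 27 and 15. The first includes a dropout allowance and the other two do not. It does not reproduce 90 for 2-fold.

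**Hand check with the normal approximation.** Smaller-arm size = (1.960 + 0.842)² × 0.32² × (1 + 1/2) / (log10 fold)². For 2-fold this is 7.849 × 0.1024 × 1.5 / 0.0906 = 13.3, rounded up to 14, so 14 × 3 = 42. For 1.6-fold it is 28.9, rounded up to 29, so 87. The t-test raises that to 90.

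**Other readings of 90 for a 2-fold reduction:**

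- *1:1 allocation:* 19+19 = 38.
- *Enrolled rather than evaluable:* 42 × 1.2 gives 51, and 42 / 0.8 gives 53. For 90 enrolled to leave 42, dropout would have to be 1 − 42/90 = 53%.
- *Higher power:* 57 for 90% and 69 for 95%.
- *Larger SD:* about 0.475 with 90 evaluable, or about 0.42 with 72 evaluable, against the stated 0.32.

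**What 90 patients would deliver at 2:1:**

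| Reading of 90 | Evaluable | Power for 2-fold | Fold detectable at 80% power |
|---|---|---|---|
| All evaluable | 60:30 | 98.6% | 1.59 |
| 90 / 1.2 = 75 | 50:25 | 96.6% | 1.67 |
| 90 × 0.8 = 72 | 48:24 | 96.0% | 1.69 |

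**Cross-check on the method.** Section 6.1 also gives detectable B-cell reductions of 2.7-fold (SD 0.76) and 3.5-fold (SD 0.97) with 144 patients and 20% dropout. With 144 × 0.8 ≈ 115 evaluable (77:38), the same t-test gives 2.67 and 3.49, which supports the 2:1 ratio.

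**The case against.** The strongest objection is that nothing depends on this number. It sits in a contingency sentence for an optional substudy, and the planned 144 for 1.5-fold is not in dispute. No rule in Appendix 18 uses the fallback sizes, and item 6 of the clarification letter classes the Appendix 18 analyses as exploratory. The printed figure is conservative. It can no longer guide recruitment either: SAP Section 2.2 records that "67 additional patients were randomized from April 2022 to August 2022", and entry to the substudy needed a lumbar puncture before the first ocrelizumab dose. All of this stands, and it limits the point to a minor correction.

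A second objection is that the match to the neighbouring figures relies on inferred conventions. The sizes 27 and 15 appear only with exact 2:1 arms and no dropout allowance. With a near-2:1 split, 25 (16:9, 81.5%) and 13 (8:5, 85.1%) would already reach 80%. The 144 fits as 120 × 1.2, whereas 120 / 0.8 would be 150, and 144 × 0.8 ≈ 115 evaluable (77:38) gives 78.6% power for 1.5-fold. The B-cell figures match on × 0.8. Section 6.1 therefore does not follow one visible dropout rule, and the allocation ratio is reached only by cross-reference. This weakens the supporting pattern but not the finding, because 90 for 2-fold fails under every convention tried.

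The planned mixed model for repeated measures does not explain the gap, since the other printed NfL sizes fit the simpler t-test.

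**Conclusion.** The point holds. On the protocol's own inputs, a 2-fold reduction in CSF NfL needs about 42 evaluable patients at 2:1 (38 at 1:1), so the printed 90 is roughly twice too large. Equivalently, 90 evaluable patients correspond to a 1.6-fold reduction. This rests on SD 0.32, two-sided 5%, 80% power and a t-test approximation. The 2:1 ratio affects the exact figure but not the conclusion. Which half of the pair was mis-entered cannot be settled from the documents. Severity is low: this is a question of accuracy in the protocol text, with no effect on patients, enrolment or any planned test.

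**What to change.** Correct whichever half of the pair is wrong, from the sponsor's original calculation: either about 42 subjects for a 2-fold reduction, or 90 subjects for a 1.6-fold reduction.

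Two drafting improvements could go in at the same time, though neither corrects this error. First, label the fallback sizes as evaluable patients from a t-test approximation. Second, if enrolled sizes are also given, apply the dropout rule used for 144 and state it.

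The cost is protocol wording only, with no change to enrolment or analysis. The clarification letter already expects its changes to be carried into any future amendment, and this correction can go with them.

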6.2 SAFETY ANALYSES

Safety will be assessed and analyzed as outlined in the main study protocols. AEs for substudy procedures will be summarized descriptively.

6.3 PHARMACOKINETIC ANALYSES

Individual and mean CSF ocrelizumab concentration will be listed and summarized by visit and treatment arm. Graphical summaries may be presented. CSF concentration values collected as part of the substudy will be compared to serum ocrelizumab PK collected in the same patient as part of the main studies.

Additional PK analyses will be conducted as appropriate.

6.4 BIOMARKER ANALYSES

Biomarkers will be assessed at baseline and subsequent timepoints following administration of ocrelizumab. Biomarker levels will be presented as absolute values over time and/or changes relative to baseline over time. The relationship between changes in efficacy and safety parameters and levels of biomarker may be examined to assess the predictive properties of biomarkers and their ability to identify patients who might benefit from higher dose of ocrelizumab versus the approved dose. Descriptive or summary statistics will be used to describe biomarker assessments.

6.5 INTERIM ANALYSIS

Refer to the main study protocol for Study BN42082 for the details regarding the interim analysis.

7. DATA COLLECTION AND MANAGEMENT

Refer to the main study protocol for Study BN42082 for the details on data collection and management.

8. ETHICAL CONSIDERATIONS

8.1 COMPLIANCE WITH LAWS AND REGULATIONS

Refer to Section 8.1 of the main study protocol for Study BN42082 for the details regarding compliance with laws and regulations.

8.2 INFORMED CONSENT

A separate ICF must be signed by the patients to participate in this optional substudy.

Refer to Section 8.2 of the main study protocol for Study BN42082 for the details on the Informed Consent process and requirements.

8.3 INSTITUTIONAL REVIEW BOARD OR ETHICS COMMITTEE

Refer to Section 8.3 of the main study protocol for Study BN42082 for the details on IRB/ECs.

8.4 CONFIDENTIALITY

Refer to Section 8.4 of the main study protocol for Study BN42082 for the details on confidentiality.

8.5 FINANCIAL DISCLOSURE

Refer to Section 8.5 of the main study protocol for Study BN42082 for the details on financial disclosure.

8.6 STUDY DOCUMENTATION, MONITORING, AND ADMINISTRATION

Refer to the main study protocol for Study BN42082 for the details on study documentation.

8.7 PROTOCOL DEVIATIONS

Refer to the main study protocol for Study BN42082 for the details on protocol deviations.

8.8 MANAGEMENT OF STUDY QUALITY

Refer to the main study protocol for Study BN42082 for the details on the management of study quality.

8.9 SITE INSPECTIONS

Refer to the main study protocol for Study BN42082 for the details on site inspections.

8.10 ADMINISTRATIVE STRUCTURE

This trial will be sponsored and managed by F. Hoffmann-La Roche Ltd. The Sponsor will provide clinical operations management, data management, and medical monitoring.

This substudy will be conducted at the interested sites amongst the approximately 220 sites participating in the main study and will enroll up to 144 patients with RMS. Enrollment will occur through an IxRS.

Central facilities will be used for certain study assessments throughout the study (e.g., specified laboratory tests, biomarker, and PK analyses), as specified in Section 4.5.3.

An iDMC will be employed to monitor and evaluate patient safety throughout the study.

8.11 DISSEMINATION OF DATA AND PROTECTION OF TRADE SECRETS

The results of this study may be published or presented at scientific congresses. For all clinical trials in patients involving an investigational medicinal product (IMP) for which a marketing authorization application has been filed or approved in any country, the Sponsor aims to submit a clinical study report and journal manuscript regarding the results of the substudy, as per the Roche publication guidelines. In addition, for all clinical trials in patients involving an IMP for which a marketing authorization application has been filed or approved in any country, the Sponsor aims to publish results from analyses of additional endpoints and exploratory data that are clinically meaningful and statistically sound.

The investigator must agree to submit all manuscripts or abstracts to the Sponsor prior to submission for publication or presentation. This allows the Sponsor to protect proprietary information and to provide comments based on information from other studies that may not yet be available to the investigator.

In accordance with standard editorial and ethical practice, the Sponsor will generally support publication of multicenter trials only in their entirety and not as individual center data. In this case, a coordinating investigator will be designated by mutual agreement.

Authorship will be determined by mutual agreement and in line with International Committee of Medical Journal Editors authorship requirements. Any formal publication of the study in which contribution of Sponsor personnel exceeded that of conventional monitoring will be considered as a joint publication by the investigator and the appropriate Sponsor personnel.

Any inventions and resulting patents, improvements, and/or know-how originating from the use of data from this study will become and remain the exclusive and unburdened property of the Sponsor, except where agreed otherwise.

Refer to Section 9.6 of the main study protocol for Study BN42082 for further details.

8.12 PROTOCOL AMENDMENTS

Refer to the main study protocol for Study BN42082 for the details regarding protocol amendments.

Appendix A Schedule of Activities

	Screen	Double-Blind Period														Delayed Dosing Visit	Unsched Visit	Tx Discon Visit
Dose		1			2		3		4		5		6		N ^d			
Visit	1	2 (BL)	3	4	5	6	7	8	9	10	11	12	13	n ^d	N			
Weeks		0	2	12	24	36	48	60	72	84	96	108	120	n	n+12 wks			
Window in days for substudy procedures	As for main study	-7			-7													
Main study visits ^a	x	x	x	x	x	x	x	x	x	x	x	x	x	x	x	x	x	x
Informed consent for the substudy	x																	
Review of eligibility criteria																		
Biomarker serum sample ^b		x			(x)		x											(x) ^h
CSF collection for cellular and fluid biomarker, and PK analysis ^{c, d}		x			(x)		x											(x) ^h
Whole blood collection for flow cytometry ^e		x			(x)		x											(x) ^h
Blood for PBMC ^f		x	x	x	(x)		x		x		x		x		x		x	x
Adverse event collection ^g		x	x	x	x	x	x	x	x	x	x	x	x	x	x	x	x	x

BL = baseline; CSF = cerebrospinal fluid; Discon = discontinued; MRI = magnetic resonance imaging; N = dosing visit; n = non-dosing visit; OCB = oligoclonal bands; PBMC = peripheral blood mononuclear cell; PK = pharmacokinetic; Screen = screening; SoA = schedule of activities; Tx = treatment; Unsched = unscheduled; wks = weeks.

^a Patients in the substudy should follow all main study procedures as outlined in the main study SoA [Appendix 1](#)

^b Blood sample for serum to be collected before ocrelizumab infusion and prior to methylprednisolone (or equivalent) injection at baseline, Week 24 (optional), and Week 48. Blood should be collected on same day of CSF collection to facilitate OCB/IgG Index measurement.

^c CSF collection to be performed before ocrelizumab infusion and prior to methylprednisolone (or equivalent) injection at baseline, Week 24 (optional), and Week 48. CSF samples to be collected on same day of blood collection to facilitate comparison to OCB/IgG Index and PK measurements (PK will only be measured in post-dose samples).

- ^d The collection of the CSF specimen at baseline should ideally not occur within the first 10 days of the brain MRI at screening (and not earlier than 6 days following the brain MRI at screening), to avoid contamination with gadolinium in the biomarker CSF sample. The collection of the CSF specimen should precede the brain MRI at Week 24 and Week 48, to avoid contamination with gadolinium in the biomarker CSF sample. In order to facilitate scheduling before an ocrelizumab dose (e.g., at Week 24 or Week 48), the CSF specimen, followed by the brain MRI, may precede the administration of ocrelizumab by up to 7 business days.
- ^e A fresh whole blood sample to be collected on the same day of CSF collection to be processed locally with CSF for flow cytometry analysis. Blood sample should be collected prior to the methylprednisolone injection if at a dosing visit and will be drawn for baseline and indicated post-dose samples.
- ^f PBMC cells will be collected from two fresh whole blood samples at indicated timepoints in Schedule of Assessments and sent to the central lab for processing. PBMC samples should be collected prior to the methylprednisolone injection if at a dosing visit and will be drawn for baseline and indicated post-dose samples.
- ^g Adverse events resulting from any substudy procedure (e.g., lumbar puncture, blood draw) should be recorded at any visit, as close to the occurrence of the event as possible.
- ^h Patients will be asked to give optional treatment discontinuation CSF and matched blood samples, if no other post-dose samples have been collected.

